## Statistical Plan and Data Analysis

The randomized groups will be descriptively compared on baseline demographic and pain variables using descriptive statistics. In particular, groups will be considered well-balanced on a particular baseline variable if the standardized difference (difference in means or proportions divided by the pooled standard deviation) is less than  $\sqrt{2/n}$ , where  $n$  is the per-group sample size. The primary analysis will be modified intention-to-treat, in which all randomized subjects who received any of the study treatment will be included and retained in their respective treatment groups.

**Aim 1: Primary outcome.** We will assess the average causal effect of cryoneurolysis versus sham/placebo on phantom limb pain intensity (average pain over past 72 hours) at 4 months after the initial treatment using analysis of covariance to adjust for baseline pain intensity and any imbalanced baseline variables (see above). Results will be summarized as the least squares difference in means at 4 months and 95% confidence interval. Mean and standard deviation change from baseline intensity will also be summarized. Similar analyses will be conducted for the secondary outcomes of current/present, worst and least phantom pain, as well as average and worst residual limb pain.

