**Crossover phase.** Beginning 4-6 months after the original randomization, requesting subjects will receive the opposite treatment from that received in their original randomization, and the same measurements will be collected through 4 months (see **Table 1**). This option will allow all subjects the opportunity to receive the study treatment. Although a completely unbiased assessment of the average causal effect will not be possible for this phase because the second treatment will be

[figure not shown]
voluntary, and crossover will thus likely be requested more often from those receiving sham/placebo in the first phase, we will still descriptively report the average treatment effect from those choosing to cross over (but no testing will be done; unbiased average causal effect will be obtained from the first phase).

More importantly, we will estimate the variability in the individual causal effects of cryoneurolysis versus sham/placebo using this crossover design. Variability of the individual causal effects cannot be directly estimated in a parallel group study (e.g., from the main portion (Aim 1) of this study we can only directly estimate the average causal effect), since only the outcome for the single treatment received is measurable for each subject. However, estimation of the variability of the individual causal effects from the crossover study, quantified as the standard deviation of within-subject differences on treatment versus sham/placebo, will provide valuable information about the heterogeneity of the treatment effect across subjects associated with cryoneurolysis treatment of phantom limb pain. We will also use regression models to explore whether any baseline factors are associated with higher or lower causal effects of treatment.

**Long-term follow-up.** Data for all outcomes will also be collected at 12 months post randomization. Due to the crossover design, we will not be able to directly assess the treatment effect of cryoneurolysis versus sham on these outcomes. Rather, we will descriptively assess the change from the initial baseline to 12 months for various groups of subjects: 1) all who received the active treatment either initially or in the crossover, 2) initial control subjects who were not crossed over; 3) initial control subjects who were crossed over; 4) initial treated subjects who were not crossed over; 5) initial treated subjects who were crossed over.

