**Dropouts.** At most, about 7% of subjects in each group are expected to drop out of the study before reaching the 4-month primary outcome assessment (based on an unpublished pilot study of pre-emptive continuous peripheral nerve block use for surgical amputation, for which we observed 1 of 15). Since the current study will consist of volunteers traveling to the centers for enrollment and a treatment procedure, we expect even less. For those missing 4-month data we will use the last-observation-carried-forward method if the brief pain inventory was measured at 3 months. Otherwise, we will use intent-to-treat and conservatively assign the best observed score to the sham/control group and the worst score for the treated group subjects. We do not expect any appreciable effect of dropouts on either the power of the study or the unbiasedness of study results.

**Interim analyses.** We will conduct interim analyses to assess efficacy (rejecting null) and futility (rejecting alternative) at each 25% of the maximum enrollment using a group sequential procedure. Specifically, a gamma spending function will be used with parameters -4 and -2 for efficacy and futility, respectively. Thus, boundaries at the 1st through 4th analyses for efficacy (futility in parentheses) will be  $P \leq 0.0016$  ( $P > 0.9572$ ),  $P \leq 0.0048$  ( $P > 0.7186$ ),  $P \leq 0.0147$  ( $P > 0.2389$ ) and  $P \leq 0.0440$  ( $P > 0.0440$ ) (**Figures below**).

**Type I error.** We will use a parallel gatekeeping procedure to control the study-wide type I error at 0.05. For this procedure, we therefore *a priori* prioritize the study outcomes into ordered sets, as Aim 1, Aim 2a, Aim 2b and then Aim 2c. Analysis will proceed in that order, and testing will proceed through each “gate” to the next set if and only if at least one outcome in the current set reaches significance. The significance level for each set will be 0.05 times a cumulative penalty for non-significant results in previous sets (i.e., a “rejection gain factor” equal to the cumulative product of the proportion of significant tests across the preceding sets). Within a set, a multiple comparison procedure (Bonferroni correction) will be used as appropriate to control the type I error at the appropriate level. SAS statistical software (Carey, North Carolina), R programming language (The R Project for Statistical Computing) and East 5.3 software (Cytel Inc.) will be used for all analyses.

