**Sample size considerations.** Our sample size estimate is based on the primary specific aim of whether the addition of cryoneurolysis decreases phantom limb pain intensity resulting from an amputation compared with current standard-of-care treatment at 4 months following cryoneurolysis. Receiver operating characteristic curve analyses demonstrate that changes from baseline of at least 1.7 along a 10-point NRS accurately identified patients who rated improvements as “much improved” or more, compared with those who perceived no change or worsening following analgesic interventions. Multiple additional studies confirm this degree of reduction as clinically meaningful to individual patients with chronic pain. Meaningful group differences in the mean change would be somewhat smaller than important changes for individuals.

Therefore, we power our study to be able to detect group differences in mean change from baseline of 1.7 points or more on the NRS. Based on a conservative standard deviation estimate for each group of 3.0 at 4 months, a correlation of 0.50 between baseline and follow-up NRS, a two-sided test at the 0.05 significance level, power of 0.90, and 4 equally spaced analyses (3 interim and 1 final, as needed), a maximum of 72 subjects in each group (N=144 total) is required (East 5.3 software, Cytel Inc). The expected sample size for this group sequential design (i.e., average sample size over thousands of such trials, stopping when a boundary is crossed) is a total of 100 under the alternative and 102 under the null hypotheses. **Table 2** reports boundary crossing probabilities at each of the 4 analyses for this design, assuming that either the null or alternative hypotheses were true. For example, there is a cumulative 8%, 37% and 75% chance of crossing a boundary at the 1st, 2nd and 3rd analyses, respectively, if the alternative hypothesis were true. However, if the true standard

deviation at 4 months were smaller, say 2.5 instead of 3.0, then the cumulative probability of stopping for efficacy at the 1st, 2nd and 3rd analyses, respectively, would increase to 16%, 55% and 88% under the alternative hypothesis.

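### The primary result is planned as an unadjusted mean difference with a 95% CI in a four-look group sequential trial, so the estimate runs high at the design alternative and the interval can disagree with the final boundary

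*Combined protocol and SAP*

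**What the plan says.** All references are to section 9 of the combined protocol and SAP.

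- *Aim 1: Primary outcome* plans an analysis of covariance and says: "Results will be summarized as the least squares difference in means at 4 months and 95% confidence interval". It does not say how the interval is built.
- *Interim analyses*: "We will conduct interim analyses to assess efficacy (rejecting null) and futility (rejecting alternative) at each 25% of the maximum enrollment". Further: "Specifically, a gamma spending function will be used with parameters -4 and -2 for efficacy and futility, respectively". The efficacy boundaries are P ≤ 0.0016, 0.0048, 0.0147 and 0.0440. The futility boundaries are P > 0.9572, 0.7186 and 0.2389, with 0.0440 at the end.
- *Sample size considerations* and Table 2 give a maximum of 72 per group, two-sided alpha 0.05, power 0.90, and a 75% chance under the alternative of crossing some boundary by the third look.
- *Type I error* names East 5.3 among the software. Nowhere does the plan mention a bias-adjusted or median-unbiased estimate, a repeated or stage-wise interval, an adjusted P value, or a confidence level matched to the boundary.

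**The concern.** When the data decide when a trial stops, the ordinary mean difference and its ordinary 95% CI no longer have their fixed-sample properties at every true effect. Efficacy stops select high estimates and futility stops select estimates near zero. Under this plan's own alternative most trials stop early, so the published effect in NRS points, which readers will compare with the plan's 1.7-point benchmark, would tend to be too large.

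There is also a mismatch between interval and test. An ordinary 95% CI excludes zero when P < 0.05, but the final look requires P ≤ 0.0440. Between the two, the interval and the formal decision point in opposite directions. Because testing of Aims 2a to 2c depends on Aim 1 reaching significance, how such a result is reported should be settled in advance.

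**Working it through.** **Inputs** (*Sample size considerations*, *Interim analyses*, Table 2). Effect: "group differences in mean change from baseline of 1.7 points or more on the NRS". SD: "Based on a conservative standard deviation estimate for each group of 3.0 at 4 months". Baseline to follow-up correlation 0.50; 72 per group at most; looks at 25, 50, 75 and 100%.

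**Which SD.** At correlation 0.50 the change-score SD is √(2 × 9 × (1 − 0.5)) = 3.0. The planned ANCOVA has residual SD 3.0 × √(1 − 0.25) = 2.598. Both are carried below.

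**Reproducing the plan's design.**
- Alpha spent at fraction t is 0.05 × (e^(4t) − 1)/(e^4 − 1) = 0.0016, 0.0060, 0.0178, 0.0500. Beta spent is 0.10 × (e^(2t) − 1)/(e^2 − 1) = 0.0102, 0.0269, 0.0545, 0.1000. Both match Table 2.
- Critical values from the stated P values: |Z| ≥ 3.156, 2.820, 2.440, 2.014 for efficacy; |Z| < 0.054, 0.360, 1.178 for futility.
- The final SE at SD 3.0 is 3.0 × √(2/72) = 0.50, so the drift is 1.7/0.50 = 3.4.
- Numerical integration gives power 0.900, stopping probabilities 0.083/0.290/0.380/0.247 under the alternative (plan: 0.083/0.290/0.379/0.248), and expected N 100.4 and 102.3 (plan: 100 and 102).
- Two-sided alpha is 0.0499 with futility non-binding and 0.0457 with futility obeyed.

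**Smallest estimate that can cross for efficacy** (SD 3.0). With SE = 0.50/√t = 1.000, 0.707, 0.577, 0.500, the critical value times SE is 3.16, 1.99, 1.41 and 1.01. A stop at look 1 therefore cannot report less than 3.16.

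**Unadjusted estimate and 95% CI at stopping, true effect 1.7** (2 to 4 million simulated trials per scenario; normal data, known variance):

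| | SD 3.0 | SD 2.598 |
|---|---|---|
| Bias, futility obeyed | +0.17 (10%) | +0.18 |
| Coverage, futility obeyed | 92.4% | 93.4 to 93.5% across runs |
| Bias, futility not obeyed | +0.21 | +0.20 |
| Coverage, futility not obeyed | 94.0% | 94.4% |
| Mean estimate, early efficacy stops | 2.21 | 2.05 |
| Mean estimate, efficacy stop at look 1 | 3.60 | 3.16 |
| Coverage, efficacy stop at look 1 | 66% | about 78% |

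At SD 3.0 about 70% of trials stop early for efficacy (about 7% at look 1). Coverage among all of these is about 95%: 66% at look 1, 96.4% at look 2, 99.9% at look 3.

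**Other true effects** (SD 3.0, futility obeyed):
- Effect 0: bias 0, coverage 95.0%.
- Effect 0.5: bias −0.06, coverage 94.6%.
- Effect 1.0: bias about 0, coverage 94.4 to 94.5%. The 25% of these trials that stop early for efficacy average 1.95, with 84% coverage.
- Effect 2.2: bias +0.23, coverage 94.4%.

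**Interval against boundary.** At the final look the conflict needs |Z| between 1.960 and 2.014, an estimate between 1.960 × 0.50 = 0.98 and 2.014 × 0.50 = 1.01. Its probability (SD 3.0, futility obeyed) is 0.4% at effect 0, 1.5% at 0.85, about 1.6% at 1.0 and 0.6% at 1.7.

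**After the fix** (stage-wise ordering, futility non-binding, SD 3.0, illustrative Z values; the adjusted point estimate shown is the median-unbiased one):

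| Look, Z | Unadjusted | Stage-wise |
|---|---|---|
| 2, 2.90 | 2.05 (0.66 to 3.44) | 2.04 (0.63 to 3.48) |
| 3, 2.50 | 1.44 (0.31 to 2.57) | 1.43 (0.27 to 2.61) |
| 4, 2.00 | 1.00 (0.02 to 1.98), P 0.0455 | 0.99 (−0.005 to 2.00), P 0.051 |

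The last row now agrees with the missed boundary. The median-unbiased estimate hardly moves. A mean-bias-adjusted estimate reduces the overall bias at effect 1.7, SD 3.0, from +0.17 to +0.03. Merely using a 95.6% interval (1 − 0.044) removes the final-look conflict, but coverage at 1.7 is still 93.3% and the bias is unchanged.

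**The case against.** The strongest reply is that the test is sound and the defect is small. Decisions rest on P boundaries that reproduce alpha 0.05, no section makes the 95% CI a decision rule, and the conflict window is narrow. The plan is silent on how the interval is built; it does not expressly choose a fixed-sample one. Stage-wise correction moves typical estimates by only 0.01 points. All of this stands, and it limits the severity.

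Stronger readings are tempting, but the documents do not support them:

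- *The estimate is always biased and the interval always under-covers.* At effect 0 there is neither; at 1.0 (SD 3.0) overall bias is about nil; for smaller effects it is slightly negative if futility is obeyed; and at 2.2 with SD 2.598 coverage is 95.8%.
- *A wrong interval is the expected outcome, given the 75% chance of an early stop.* That 75% includes about 5% futility stops, and intervals after early efficacy stops at 1.7 cover about 95% overall. Only look 1 is clearly poor. Elsewhere the harm is the inflated estimate.
- *The plan contradicts itself where it says "unbiased average causal effect will be obtained from the first phase".* That sentence, under *Crossover phase*, contrasts randomized assignment with voluntary crossover. It concerns selection and makes no claim about sequential stopping, so it can stay.

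What the reply does not answer is that an unqualified least squares difference and 95% CI reads as the ordinary summary, and nothing in the plan prevents it from being reported after an early stop.

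**Conclusion.** The concern holds as a should-fix reporting gap. Followed on its plain reading, the plan overstates the effect at its own alternative by about 0.17 to 0.18 NRS points overall if futility stops are obeyed (0.20 to 0.21 if not). Among trials stopping early for efficacy the excess is 2.21 − 1.7 = 0.51 (SD 3.0) or 2.05 − 1.7 = 0.35 (SD 2.6). The shortfall in coverage is 0.6 to 2.6 percentage points, depending on the SD and on whether futility stops are obeyed. The interval can contradict the final boundary in about 0.4% to 1.6% of trials for effects from 0 to 1.7. Type I error, power and sample size are not affected.

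These figures assume normal outcomes with known variance, exactly equal looks, full accrual of 72 per group if there is no stop, and the plan's SD and correlation. The size depends on the true effect.

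**What to change.** Under *Aim 1: Primary outcome*:

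1. State that the primary 95% CI and P value will be group sequential, by stage-wise ordering, at the look where the trial stops, so that they agree with the efficacy boundary. Say whether the calculation treats futility as binding, because exact coverage requires it to match conduct.
2. Report a bias-adjusted estimate, for example mean-bias-adjusted, beside the ANCOVA least squares difference.
3. Label secondary estimates taken after an early stop as unadjusted for stopping.

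The repeated CI is a conservative alternative, not the first choice. It covers 98.9% at effect 1.7 and at look 2 (SD 3.0) has half-width 2.820 × 0.707 = 1.99 instead of 1.960 × 0.707 = 1.39.

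The cost is a few sentences and standard group sequential output, with a slightly wider interval and a somewhat smaller estimate after an early stop. Design, sample size and conduct do not change. The wording should be settled before the first interim look.

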### **Secondary outcomes.**

**Aim 2a.** The randomized groups will be compared on the global measure of improvement (Patient Global Impression of Change Scale) at 4 months using the Mann-Whitney test. Proportional odds logistic regression will be used to adjust for any imbalanced baseline variables, as appropriate.

**Aim 2b.** The randomized groups will also be compared at 4 months on the seven measures of Brief Pain Inventory, which evaluate pain's interference with physical and emotional functioning. We will use a mixed effects multivariate model (random subject term, fixed treatment effect, unstructured correlation matrix) to first assess whether the treatment effect differs across the individual measures (i.e., treatment-measure interaction). In presence of an interaction, each measure will be evaluated univariably. Otherwise, an overall treatment effect will be estimated from the mixed effects model as the primary result for this aim.

**Aim 2c.** Analysis of covariance adjusting for baseline score will be used to assess the treatment effect of cryoneurolysis versus sham on depression at 4 months after randomization as measured by the Beck Depression Inventory.

**Blinding assessment.** To assess the quality of the subject blinding as to initial treatment assignment, we will ask each subject on Day 0 to speculate which treatment they received (actual or sham cryo). A Pearson's chi-square test will be used to compare the proportion of correct speculations in each treatment group.

For all analyses, alternative statistical methods will be used if the assumptions of the planned analyses are not met. For instance, t-tests or regression analyses on the change or percent change from baseline (depending on which is less correlated with baseline score) will be used instead of analysis of covariance when comparing groups on the 4-week outcomes if the treatment group-by-baseline interaction is significant. Transformations of the data or Mann-Whitney test or other non-parametric procedures will be used if the assumptions of normality and/or equal variances are not met.

**Crossover phase.** Beginning 4-6 months after the original randomization, requesting subjects will receive the opposite treatment from that received in their original randomization, and the same measurements will be collected through 4 months (see **Table 1**). This option will allow all subjects the opportunity to receive the study treatment. Although a completely unbiased assessment of the average causal effect will not be possible for this phase because the second treatment will be

[figure not shown]
voluntary, and crossover will thus likely be requested more often from those receiving sham/placebo in the first phase, we will still descriptively report the average treatment effect from those choosing to cross over (but no testing will be done; unbiased average causal effect will be obtained from the first phase).

More importantly, we will estimate the variability in the individual causal effects of cryoneurolysis versus sham/placebo using this crossover design. Variability of the individual causal effects cannot be directly estimated in a parallel group study (e.g., from the main portion (Aim 1) of this study we can only directly estimate the average causal effect), since only the outcome for the single treatment received is measurable for each subject. However, estimation of the variability of the individual causal effects from the crossover study, quantified as the standard deviation of within-subject differences on treatment versus sham/placebo, will provide valuable information about the heterogeneity of the treatment effect across subjects associated with cryoneurolysis treatment of phantom limb pain. We will also use regression models to explore whether any baseline factors are associated with higher or lower causal effects of treatment.

**Long-term follow-up.** Data for all outcomes will also be collected at 12 months post randomization. Due to the crossover design, we will not be able to directly assess the treatment effect of cryoneurolysis versus sham on these outcomes. Rather, we will descriptively assess the change from the initial baseline to 12 months for various groups of subjects: 1) all who received the active treatment either initially or in the crossover, 2) initial control subjects who were not crossed over; 3) initial control subjects who were crossed over; 4) initial treated subjects who were not crossed over; 5) initial treated subjects who were crossed over.

**Dropouts.** At most, about 7% of subjects in each group are expected to drop out of the study before reaching the 4-month primary outcome assessment (based on an unpublished pilot study of pre-emptive continuous peripheral nerve block use for surgical amputation, for which we observed 1 of 15). Since the current study will consist of volunteers traveling to the centers for enrollment and a treatment procedure, we expect even less. For those missing 4-month data we will use the last-observation-carried-forward method if the brief pain inventory was measured at 3 months. Otherwise, we will use intent-to-treat and conservatively assign the best observed score to the sham/control group and the worst score for the treated group subjects. We do not expect any appreciable effect of dropouts on either the power of the study or the unbiasedness of study results.

**Interim analyses.** We will conduct interim analyses to assess efficacy (rejecting null) and futility (rejecting alternative) at each 25% of the maximum enrollment using a group sequential procedure. Specifically, a gamma spending function will be used with parameters -4 and -2 for efficacy and futility, respectively. Thus, boundaries at the 1st through 4th analyses for efficacy (futility in parentheses) will be  $P \leq 0.0016$  ( $P > 0.9572$ ),  $P \leq 0.0048$  ( $P > 0.7186$ ),  $P \leq 0.0147$  ( $P > 0.2389$ ) and  $P \leq 0.0440$  ( $P > 0.0440$ ) (**Figures below**).

**Type I error.** We will use a parallel gatekeeping procedure to control the study-wide type I error at 0.05. For this procedure, we therefore *a priori* prioritize the study outcomes into ordered sets, as Aim 1, Aim 2a, Aim 2b and then Aim 2c. Analysis will proceed in that order, and testing will proceed through each “gate” to the next set if and only if at least one outcome in the current set reaches significance. The significance level for each set will be 0.05 times a cumulative penalty for non-significant results in previous sets (i.e., a “rejection gain factor” equal to the cumulative product of the proportion of significant tests across the preceding sets). Within a set, a multiple comparison procedure (Bonferroni correction) will be used as appropriate to control the type I error at the appropriate level. SAS statistical software (Carey, North Carolina), R programming language (The R Project for Statistical Computing) and East 5.3 software (Cytel Inc.) will be used for all analyses.

**Sample size considerations.** Our sample size estimate is based on the primary specific aim of whether the addition of cryoneurolysis decreases phantom limb pain intensity resulting from an amputation compared with current standard-of-care treatment at 4 months following cryoneurolysis. Receiver operating characteristic curve analyses demonstrate that changes from baseline of at least 1.7 along a 10-point NRS accurately identified patients who rated improvements as “much improved” or more, compared with those who perceived no change or worsening following analgesic interventions. Multiple additional studies confirm this degree of reduction as clinically meaningful to individual patients with chronic pain. Meaningful group differences in the mean change would be somewhat smaller than important changes for individuals.

Therefore, we power our study to be able to detect group differences in mean change from baseline of 1.7 points or more on the NRS. Based on a conservative standard deviation estimate for each group of 3.0 at 4 months, a correlation of 0.50 between baseline and follow-up NRS, a two-sided test at the 0.05 significance level, power of 0.90, and 4 equally spaced analyses (3 interim and 1 final, as needed), a maximum of 72 subjects in each group (N=144 total) is required (East 5.3 software, Cytel Inc). The expected sample size for this group sequential design (i.e., average sample size over thousands of such trials, stopping when a boundary is crossed) is a total of 100 under the alternative and 102 under the null hypotheses. **Table 2** reports boundary crossing probabilities at each of the 4 analyses for this design, assuming that either the null or alternative hypotheses were true. For example, there is a cumulative 8%, 37% and 75% chance of crossing a boundary at the 1st, 2nd and 3rd analyses, respectively, if the alternative hypothesis were true. However, if the true standard

deviation at 4 months were smaller, say 2.5 instead of 3.0, then the cumulative probability of stopping for efficacy at the 1st, 2nd and 3rd analyses, respectively, would increase to 16%, 55% and 88% under the alternative hypothesis.

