of childbearing age with the possibility of pregnancy, a sample of urine will be collected before any study interventions to confirm a non-pregnant state. All subjects will have a peripheral intravenous (IV) catheter inserted, standard noninvasive monitors applied (blood pressure cuff, pulse oximeter, 5-lead ECG), and oxygen administered via a facemask or nasal cannula. Oral and intravenous sedatives and analgesics such as Midazolam, valium and fentanyl will be titrated for patient comfort if necessary, while ensuring that patients remained responsive to verbal cues.

The specific nerves targeted will be the sciatic and femoral (or their distal branches). The potential cryoneurolysis sites will be cleansed with chlorhexidine gluconate and isopropyl alcohol. Using the optimal ultrasound transducer for the specific anatomic location and subject anatomy (linear vs curvilinear array), the target nerves will be identified in a transverse cross-sectional (short axis) view. A local anesthetic skin wheal will be raised adjacent to the ultrasound transducer and a Tuohy-tip needle will be inserted through the skin wheal in-plane beneath the ultrasound transducer and directed until the needle tip is immediately adjacent to the target nerve. Local anesthetic (1-3 mL, lidocaine 2%) will be injected in divided doses with frequent aspiration. This will be repeated for the second target nerve (either femoral or sciatic). Within 20 minutes of the second injection, the subject's limb pain level will be evaluated on the 0-10 NRS and if higher than at baseline prior to injection, the subject will NOT continue with treatment and their participation in the study will terminate upon discharge.

**Treatment group assignment (randomization).** Remaining subjects will be allocated to one of two possible treatments:

1. *cryoneurolysis*
2. *sham cryoneurolysis (placebo control)*

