**Additional pain-related data.** Frequency and average duration of non-painful phantom sensations, phantom limb pain, and residual limb pain will be assessed. In addition, supplemental analgesic use will be recorded, and other pain locations/severity will be evaluated using the NRS. Lastly, to investigate masking adequacy, subjects will be queried on Day 0 following the treatment procedure on which treatment they believe they received (active cryoneurolysis vs. sham/placebo).

**Data collection.** Subject demographic and cryoneurolysis administration data will be uploaded from each enrolling center *via* the Internet to a secure, password-protected, encrypted central server (RedCap, Cleveland Clinic, Cleveland, Ohio). The questionnaires for all subjects—regardless of enrolling center—will be administered by telephone from the University of California San Diego by research coordinators specifically trained in these instruments’ application, minimizing inter-rater discordance. Staff masked to treatment group assignment will perform all assessments. This web-based data-collection protocol has been used successfully by the investigators for numerous previously published multicenter clinical trials. Each data collection phone call will require approximately 15 minutes, with any time point including the Beck Depression Inventory requiring an additional 15 minutes.

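### The blinding test compares the rate of correct guesses between arms, which does not test whether guesses depend on treatment

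*Combined protocol and SAP*

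**What the plan says.** The Blinding assessment paragraph (Section 9, Statistical Plan and Data Analysis) gives its purpose as follows: "To assess the quality of the subject blinding as to initial treatment assignment". The data are one binary answer, active or sham. Additional pain-related data fixes the timing: "subjects will be queried on Day 0 following the treatment procedure on which treatment they believe they received". The only analysis named is that a Pearson "chi-square test will be used to compare the proportion of correct speculations in each treatment group".

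The documents give no test of guess against assignment, blinding index, 50% reference, expected guess rate, significance level or decision rule for this check. The paragraph that follows allows substitutions: "alternative statistical methods will be used if the assumptions of the planned analyses are not met".

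**The concern.** A masking check should ask whether what subjects believe depends on what they received. Comparing accuracy between arms is a different question, and it can mislead in two ways:

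- **Missed unmasking.** If both arms see through the sham to the same extent, accuracy is equal and the test finds nothing.
- **False alarm.** If guesses are unrelated to treatment but most subjects in both arms give the same answer, accuracy is high in one arm and low in the other, and the test rejects.

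The primary outcome is self-reported pain against a sham, so readers will look to this check when they interpret the result. It is the only masking analysis planned. A shared lean on Day 0 is plausible, though this is an assumption: under Enrollment, all subjects have an injection at both target nerves before randomization ("Local anesthetic (1-3 mL, lidocaine 2%) will be injected in divided doses with frequent aspiration").

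**Working it through.** **Inputs.** Arm size is the plan's maximum, from Sample size considerations: "a maximum of 72 subjects in each group". That figure reproduces. With SD 3.0 and correlation 0.50, the SD of change is √(2 × 9 × 0.5) = 3.0. A difference of 1.7 at 90% power then needs 66 per arm in a fixed design, and applying the four stated boundaries at 144 subjects gives power 0.901. The 5% level for the blinding test and all guess rates are assumptions.

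**The two null hypotheses.** Let pa and ps be the probabilities of guessing active in the active and sham arms.

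- Proportion correct: pa in the active arm, 1 − ps in the sham arm.
- Planned null: pa = 1 − ps, that is pa + ps = 1.
- Null for masking: pa = ps.

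Both hold together only at pa = ps = 0.5.

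**Single tables.** Pearson chi-square without continuity correction, 72 per arm. For equal arm sizes, χ² = (p1 − p2)² / [p̄(1 − p̄)(2/72)], where p̄ is the mean of the two proportions. The planned test takes p1 and p2 as the proportions correct; the guess-by-arm test takes them as the proportions guessing active. Worked example, 42/72 guessing active in each arm: correct guesses are 42/72 and 30/72, p̄ = 0.5, and χ² = (12/72)² / (0.25 × 2/72) = 4.0, P = 0.046. The guess-by-arm χ² is 0.

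| Pattern | Correct, active / sham | Planned P | Guess-by-arm P |
|---|---|---|---|
| Equal unmasking | 50/72, 50/72 | 1.0 | 3 × 10⁻⁶ |
| Equal unmasking, extreme | 65/72, 65/72 | 1.0 | 4 × 10⁻²² |
| Shared lean, 41 guess active per arm | 41/72, 31/72 | 0.096 | 1.0 |
| Shared lean, 42 per arm | 42/72, 30/72 | 0.046 | 1.0 |
| Shared lean, 43 per arm | 43/72, 29/72 | 0.020 | 1.0 |
| Shared lean, 50 per arm | 50/72, 22/72 | 3 × 10⁻⁶ | 1.0 |
| One arm unmasked, other at 50% | 58/72, 36/72 | 0.0001 | 0.0001 |

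In the last row the two tests are identical, because 36/72 is both the proportion correct and the proportion guessing active in the sham arm. If every subject guesses correctly, the planned statistic is undefined because one margin is zero.

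**Rejection rates.** Exact enumeration of all 73 × 73 pairs of binomial outcomes, 5% level:

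| True state | Planned test | Guess-by-arm test |
|---|---|---|
| Masked, 50% guess active in both arms | 5% | 5% |
| Masked, 55% in both | 24% | 5% |
| Masked, 60% in both | 69% | 5% |
| Masked, 70% in both | 99.9% | 5% |
| Unmasked, 60% correct in both | 5% | 69% |
| Unmasked, 70% correct in both | 5% | 99.9% |

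**Smaller trial.** The plan expects about 100 subjects under the alternative. With a 60% shared lean and perfect masking, the planned test rejects 54% of the time at 50 per arm and 38% at 36 per arm (a stop at the second look). The guess-by-arm test has the same 54% and 38% when 60% are correct in both arms.

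**The case against.** The strongest reply is that the data already show what the P value hides. With a binary guess and known arm sizes, the two proportions correct determine the whole guess-by-arm table. A reader who sees 90% and 90% will recognize unmasking, and one who sees 70% and 30% will recognize a shared lean. Harm requires reading the P value alone, and the plan does not say that a non-significant result means adequate masking. This is right as far as it goes. But the plan does not promise to report the proportions, and the P value it does plan answers the wrong question.

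Other points have some force:

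- **Scale.** The main figures use the maximum sample size and assumed guess rates. At smaller sizes the rates fall, but the direction does not change. The 65/72 example is an illustration; because the probes look alike and both arms receive lidocaine, 55% to 60% is the more relevant range.
- **Wording.** The sentence could mean testing each arm against 50%. Equal unmasking would then be found, but a shared lean would still be flagged: 54/72 against 50% gives χ² = 18, P = 2 × 10⁻⁵. No 50% reference appears, and a two-arm comparison is the natural reading.
- **Fallback clause.** It covers failed assumptions. The chi-square assumptions can hold while the hypothesis is the wrong one.

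**Conclusion.** The concern holds. As written, the test has the wrong null hypothesis for its stated purpose. The algebra needs no assumption; the size of the effect depends on the assumed guess rates and 5% level. At 72 per arm, a modest shared lean of 55% to 60% raises the chance of a false alarm from about 5% to between 24% and 69%, while equal unmasking of any degree is detected at about the 5% chance rate. The test behaves properly when only one arm is unmasked and the other guesses at 50%.

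The consequence is confined to the conclusion about masking. The primary analysis of covariance, the gatekeeping sequence (Aims 1, 2a, 2b and 2c only), the sample size and the stopping boundaries are unaffected. The sentence should be corrected, but the fault does not threaten the primary result.

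**What to change.** Replace the test sentence under Blinding assessment, before unmasking, with: *The proportion of subjects guessing active cryoneurolysis will be compared between arms (Pearson chi-square on guess by arm). For each arm, the proportion correct and a blinding index (2 × proportion correct − 1) will be reported with 95% confidence intervals.* It would help to add that a non-significant P value alone will not be taken as proof of masking.

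The guess-by-arm test is the correction. The index only rescales the proportion correct, but it makes the pattern visible. With Wald intervals, 65/72 correct in each arm gives +0.81 (0.67 to 0.94) in both arms; 50/72 guessing active in each arm gives +0.39 (0.18 to 0.60) in the active arm and −0.39 (−0.60 to −0.18) in the sham arm. A Wald interval has zero width if every guess in an arm is correct, so an exact binomial interval, rescaled, is safer.

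The cost is one SAP sentence. The Day 0 answers suffice, with no new data, visits or subjects.
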